2.3.2 KNOWN POTENTIAL BENEFITS

This study has not been designed to benefit the individual subjects. However, subjects in this study may experience some degree of relief from mood symptoms because of the tACS treatment. Our last trial revealed preliminary efficacy, as participants who received 10 Hz tACS stimulation showed a 50% decrease in symptoms of depression two weeks later [6].

2.3.3 ASSESSMENT OF POTENTIAL RISKS AND BENEFITS

The risks and benefits presented above are no more serious than for other clinical trials in this population. Based on the need for complementary and alternative treatments for MDD, the potential risks are worth the potential benefits. Justification as to why the risks of participation in the study outweigh the value of the information to be gained.

3. OBJECTIVE AND OUTCOME MEASURES

OBJECTIVES	ENDPOINTS	JUSTIFICATION FOR ENDPOINTS
Primary		
To determine the effect of 10 Hz tACS on brain physiology as measured with electroencephalogram (EEG).	Resting state EEG recordings taken before/after every stimulation session, as well as at a 2-week follow up visit.	The focus is to determine the mechanism of action for five consecutive days of forty-minute tACS stimulation sessions. These endpoints will allow the examination of both immediate and long-term effects of 10 Hz tACS on physiology.
Secondary		
To elucidate the relationship between change in physiology and change in clinical symptoms	Correlations between Hamilton Depression Rating Scale (HDRS), Beck Depression Inventory (BDI) and alpha oscillation power (as measured by resting state EEG recordings).	Previous work indicates that 10 Hz tACS modulates mood and physiology, but there is no clear indication that these changes are related.

4. STUDY DESIGN

4.1 OVERALL DESIGN

The design for this study is a pilot, randomized, double-blind, sham-controlled, clinical trial which will be used to investigate the mechanism of action of 10 Hz tACS in subjects with MDD, as well as determine the relationship between physiological changes and clinical changes. We are recruiting from a clinical population. Participants will be 20 males and non-pregnant females ages 18-70 with unipolar, non-

psychotic MDD, free of benzodiazepine and anticonvulsant medication, who have a HDRS-17 > 8 and are at a low risk for suicide according to the Hamilton Depression Rating Scale as well as the Columbia Suicide Severity Rating Scale (C-SSRS). All women of child-bearing potential will be asked to take a pregnancy test during the initial session to determine eligibility for the study; nursing or pregnant subjects will be excluded from participation, and all women of child-bearing potential will be required to use an appropriate form of birth control throughout their participation. These individuals will be outpatients and may or may not seek mental health care from a family practitioner, therapist, or psychiatrist.

This is a single-site, pilot clinical trial with 2 arms. Due to the Covid pandemic recruitment was slower than expected. We anticipate to complete study enrollment until 12/2022. Subjects will be randomly assigned to one of two arms: active sham stimulation or 10 Hz (alpha) tACS. We will use the XCSITE100 stimulator designed by PulvinarNeuro for investigational purposes to deliver stimulation over five consecutive days. Subjects will stay in a relaxed yet experimentally controlled state by watching a nature movie such as "Reefscape" during stimulation. The initial session (D1) and D5 will take approximately 4 hours. D2-D4 will take 90 minutes. The 2-week follow-up will take approximately 3 hours. We estimate that total participation to be approximately 17 hours.

4.2 SCIENTIFIC RATIONALE FOR STUDY DESIGN

This study is a double-blind, randomized, sham-controlled interventional study. The choice of double blind and randomization is important for the integrity of our data, especially for the clinical assessments. All individuals involved with data collection (as well as all randomized subjects) will be blind to the subject's arm assignment until all data has been collected. This will reduce implicit and explicit bias in the data collection process. In this study, subjects will be randomized in to one of two arms: active sham (i.e., placebo) stimulation or 10 Hz tACS. This is a follow-up to a previous study that compared 40 Hz tACS (control frequency), 10 Hz tACS and sham/placebo stimulation. The greatest effect was found when comparing 10 Hz tACS and sham/placebo stimulation; no effect was found with 40 Hz tACS. Furthermore, for 40 Hz tACS the study blind was compromised by stimulation-induced phosphenes, with 80% of subjects correctly guessing that they had received stimulation. As a result, we choose to further explore 10 Hz tACS in comparison to sham/placebo stimulation, omitting 40 Hz tACS as our control frequency. While having only a single control (placebo/sham) may be problematic, we have determined that our smaller, second part of this study does not require the same 3 arms as previously used, as the primary outcome is target engagement measured with the EEG and to further understand the mechanism of action of tACS in a multi-day study. In this design, our sham/placebo stimulation is active, including 80 seconds of stimulation (20 seconds ramp-in to 40 seconds of 10 Hz tACS at 1 mA with 20 seconds of ramp-out). This choice of active sham/placebo is important to mimic the skin sensations and other transient side effects associated with stimulation. Typically, stimulation side effects only last approximately a minute into stimulation; indicating that theoretically sham/placebo stimulation should be difficult to differentiate from 10 Hz tACS.

4.3 JUSTIFICATION FOR DOSE

As a continuation study, we are utilizing the exact same dosage as given before: 5 consecutive days of 40-minutes of stimulation [6]. This dosage was chosen based on a previous study, which examined transcranial direct current stimulation (tDCS) for the treatment of MDD [14].

4.4 END OF STUDY DEFINITION

The end of this study is defined as when the last subject completes the final study visit (i.e., the 20th subject completes their 2-week follow-up visit).

5. STUDY POPULATION

5.1 INCLUSION CRITERIA

In order to be eligible to participate in this study, an individual must meet all of the following criteria:

- Ages 18-70 years
- DSM-IV diagnosis of MDD; unipolar, non-psychotic
- Hamilton Rating Depression Rating Scale (HRDS-17) score >8
- Low suicide risk as determined by a score of <3 on the Suicide Item on the HDRS-17 and based on additional information from the C-SSRS (no intent)
- Capacity to understand all relevant risks and potential benefits of the study (informed consent)

5.2 EXCLUSION CRITERIA

An individual who meets any of the following criteria will be excluded from participation in this study:

- DSM-V diagnosis of moderate or severe alcohol use disorder (AUD) within the last 12 months.
- DSM-V diagnosis of moderate to severe substance use disorder (excluding tobacco) within the last 12 months.
- Current axis I mood, or psychotic disorder other than major depressive disorder
- Lifetime comorbid psychiatric bipolar or psychotic disorder
- Eating disorder (current or within the past 6 months)
- Obsessive-compulsive disorder (lifetime)
- Post-traumatic stress disorder (PTSD, current or within the last 6 months)
- Attention deficit hyperactivity disorder (ADHD, currently under treatment)
- Current use of benzodiazepines or anti-epileptic drugs
- Antidepressant drugs taken for less than 4 weeks (i.e., recently initiated)
- Neurological disorders, including but not limited to history of seizures (except childhood febrile seizures and ECT-induced seizures), dementia, history of stroke, Parkinson's disease, multiple sclerosis, cerebral aneurysm.
- Medical or neurological illness (unstable cardiac disease, AIDS, malignancy, liver or renal impairment) or treatment for a medical disorder that could interfere with study participation; comorbid neurological condition (i.e. seizure disorder, brain tumor)
- History of traumatic brain injury that required subsequent cognitive rehabilitation, or cause cognitive sequelae.
- Prior brain surgery and/or any brain devices/implants, including cochlear implants and aneurysm clips
- Current pregnancy or lactation. If the ability to become pregnant exists, unwillingness to use appropriate birth control measures during study participation

- Anything that, in the opinion of the investigator, would place the participant at increased risk or preclude the participant's full compliance with or completion of the study
- Non-English speakers

5.3 LIFESTYLE CONSIDERATIONS

Benzodiazepine use will be prohibited during this study, unless used as needed. If subjects are prescribed benzodiazepines as needed (PRN), they will be requested not to use benzodiazepines within 48 hours of any study session. Current medication intake is queried every day during the stimulation period.

5.4 SCREEN FAILURES

In the design of this study, initial phone or zoom screening procedures should identify the majority of subjects who could potentially become screen drop outs in the clinical trial. However, the phone/zoom screening process does not necessarily account for all exclusion criteria.

In the case that a subject enrolls to participate in the trial and the first interview reveals that they do not meet study criteria, the study personnel completing the interviewing process will clearly explain why the subject does not meet criteria. However, in the case that a subject does not qualify based on suicide risk, procedures will be followed to ensure subject safety.

5.5 STRATEGIES FOR RECRUITMENT AND RETENTION

This clinical trial will utilize multiple recruitment strategies to communicate this opportunity to as many potential participants as possible. Our first means is through a referral process. Participants can be referred to the study through their primary mental health care provider or family doctor during routine visits. This type of recruitment will take place in doctors' offices throughout Chapel Hill, Carrboro, Durham and Raleigh areas. We estimate that approximately 15 participants will be enrolled from the Chapel Hill/Carrboro area and 5 between Durham and Raleigh. Clinicians will be informed of inclusion criteria through email and listserv announcements and be asked to mention this clinical trial to appropriate patients and offer them a flyer/ brochure with contact information. We will also be using the UNC i2b2 to send request forms to the Carolina Data Warehouse to recruit participants who have been seen at UNC Hospitals that meet the inclusion criteria.¹

In addition to referrals through primary care providers, we will advertise the study directly to the public on websites such as ClinicalTrials.gov, studypages.com, Research For Me, frohlichlab.org and Carolinaneurostimulation.org. We will have contact information and a summary of the clinical trial posted on the [name] Lab Facebook and Twitter pages. Will we also be launching a Facebook or Instagram advertisement to identify potential patients. This advertisement will include a link to a brief screening survey on RedCap to help identify participants. We will also be using the UNC Mass email and department listserv to send out an email that has the link to the survey. All patient identifiers will be stored in REDCap

until recruitment is over. When recruitment is over, all patients who do not consent or are not eligible for participation in the study will have their responses permanently deleted in REDCap.

We will send unencrypted emails to facilitate the initial contact to potential participants. Medical information is never requested per email. All medical information is recorded through HIPAA conform Zoom meetings and RedCap surveys.

Our retention strategy includes a payment schedule of three times per subject. The subject will receive payment in form of a Visa Card at D1 (\$75). This card will be charged again on D5 (\$140), and the final follow-up session (\$40). Thus, completion of the study will result in a financial compensation of \$255.

Research personnel will be easily available for the subjects to contact via email or phone. The inclusion criteria state that each subject must be able to understand all risks and benefits associated with this study. We will be asking each subject to answer questions about the consent form to determine that the study process and the duration of participation are completely understood by all subjects. We will aim to have a specific research team member assigned to complete all sessions with the same subject. However, we will not require the same researcher to be present during stimulation sessions 2 through 4. The study team will work hard at forming rapport with the subject so they feel comfortable and willing to discuss what may be sensitive information. Retention will be quantified by the fraction of subjects coming to each scheduled session (the data from each session will be scored and documented the day of the session).

As this study requires several days of participation in a row, we will allow subjects to miss one stimulation session, if it is made up at the end of the stimulation week. If two consecutive stimulation sessions are missed, the subject will be withdrawn from participation. This schedule would permit the subject to still receive the full intervention (5 days of stimulation) without being withdrawn from the study due to unforeseen circumstances (e.g., inclement weather, car trouble). In addition, the 2-week follow-up session will be scheduled on the first day of enrollment to allow for planning but within \pm 3 days of the final day of stimulation to account for possible scheduling problems.

6. STUDY INTERVENTION

6.1 STUDY INTERVENTION(S) ADMINISTRATION

6.1.1 STUDY INTERVENTION DESCRIPTION

We will be using the XCSITE100 stimulator designed by PulvinarNeuro in the [name] Lab for investigational purposes. The device is not implanted and has not been designed for or used to support or sustain human life. This device does not have a potential for serious risk to the health, safety, or welfare of the subject. There has never been an instance of serious side-effect reported due to the use of transcranial brain stimulation.

Previous studies in the [name] lab that used the XCSITE 100 and comparable devices (i.e., the commercial, CE-certified Neuroconn Plus stimulator) have been conducted under an IDE and classified as “non-significant risk” by the full UNC IRB. The Neuroconn Plus stimulator and the XCSITE100 stimulator are electrically equivalent and provide the same stimulation. While the Neuroconn device is commercially

available, it cannot be preprogrammed for 10Hz-tACS, and is not designed for tACS clinical trials. This makes the use of the Neuroconn device not appropriate for this study.

The XSCITE100 stimulator may apply tACS for up to 40-minutes (2400 seconds) with appropriate current ramp-up at the beginning of stimulation and ramp-down at the end of stimulation. tACS may be applied for currents between 100 μ A and 2 mA (peak-to-peak for tACS). For the purposes of this study, this device will be set to deliver either sham stimulation or 10Hz-tACS. The XCSITE100 device runs on a single 9V rechargeable battery. The device itself is run through a device on a tablet. For more instructions, please see the submitted instruction manual.

The stimulator has two main components:

1. Android tablet with user interface application (i.e., App)
2. Stimulator with:
 - a. Microprocessor
 - b. Function generator chip
 - c. Voltage controlled current source
 - d. Safety circuitry

Current Sensor Circuit. A 33.2 Ω sense resistor is placed in series with the stimulation electrodes on the high side. Since high-side current sensing is used, any short circuit of the electrode terminals to ground will be detected. The stimulation current flows through this resistor and creates a voltage. The voltage across this resistor is sensed and amplified by the AD628 difference amplifier. The gain of the difference amplifier is set to 9.9039. The current sensor voltage is then shifted before it is read by the microprocessor and the hardware current safety feature.

Voltage Sensor Circuit. The differential voltage across the electrodes is measured so that the impedance can be calculated. The voltage is measured by buffering the positive electrode and negative electrode each with a unity gain op-amp circuit. The voltage output is then shifted before it is read by the microprocessor using the same level shifting circuit described in the current sensor section.

The device is equipped with 4 different stages of safety precautions, all of which protect the participant from high currents. The stages are as follows:

1. *Automatic software current cutoff.* The output of the current sensor described above is read by a microprocessor, which compares the reading to a value of ± 3 mA peak. If the current exceeds these limits, stimulation is turned off. The user is then given the option to investigate the issue, and cancel or resume the test. Since high-side current sensing is used (described above), any short circuit of the electrode terminals to ground will be detected.
2. *Automatic hardware current cutoff.* The output of the current sensor is fed into a pair of comparators which detect if the current exceeds ± 4.5 mA. If so, the fault is latched such that the relay in series with the electrodes is opened. Additionally, the microprocessor is notified of this instance through an interrupt. Upon this interrupt, the microprocessor immediately stops stimulation.
3. *Permanent hardware current cutoff.* A 5 mA fast-acting fuse is in series with the electrode connector. If the above two over-current detection methods fail, the fuse will blow, and the stimulator will no longer be electrically connected to the device.
4. *Power supply fuse.* Finally, if for any other reason the entire device draws too much current, the main power supply fuse is blown. This fuse is sized with a cutoff of 200% of steady-state operating current.

6.1.2 DOSING AND ADMINISTRATION

The research team will first measure each subject's head using the 10-20 system to determine the electrode locations. Subjects will then be fitted with the 3 electrodes for stimulation: two 5x5cm electrodes placed over F3 and F4, and one 5x7cm electrode placed over Cz. Electrodes will be carbon rubber, with Ten20 conductive paste applied. During stimulation, the subject will be in a relaxed and experimentally controlled state by watching a nature movie (such as *Reefscapes*). One session of stimulation will be performed per day, for 40-minutes. Before and after each stimulation session, an eyes open and eyes closed resting state EEG will be performed.

The stimulation waveforms used in this study are sham/placebo stimulation and 10 Hz tACS at 1 mA zero-to-peak amplitude. Sham/placebo stimulation includes 20 seconds of ramp-in to 40 seconds of 10 Hz tACS at 1 mA to 20 seconds of ramp-out, for a total of 80 seconds of stimulation. This is intended to mimic the skin sensations (e.g., itching, burning, tingling) that are experienced at the onset of stimulation, assisting with blinding the subject's assignment. 10 Hz tACS also has a ramp-in and ramp-out of 20 seconds, with 40-minutes of stimulation at an amplitude of 1 mA, for a total of 2440 seconds of stimulation.

Stimulation devices will be pre-programmed, and codes will be randomized to one of the two experimental arms. Researchers will enter the subject-specific code into the tablet that controls the XCSITE100 device and will monitor subjects during the 40-minutes of the stimulation. Research personnel will be thoroughly trained and have trainings documented on the transcranial stimulation device and will be present during all stimulation sessions. To monitor side effects of stimulation a stimulation effects questionnaire will be administered after each stimulation session.

6.3 MEASURES TO MINIMIZE BIAS: RANDOMIZATION AND BLINDING

Randomization

[name], a [name] Lab member, will randomize 20 6-digit codes, which will be used by the study coordinator and research assistants. These codes are directly linked to which treatment subjects receive (sham/placebo or 10 Hz tACS at 1 mA) and will be entered into the XCSITE tablet. The assignment of each subject cannot be determined by looking at the codes (e.g., codes are not sequential, code assignment is not based on "odd" or "even" numbers). [name] has no other responsibility in the study other than providing these randomized codes. If [name] leaves the [name] Lab, another equivalent researcher who does not work with human subjects will perform this task.

Blinding

The study is double-blind. This means that the subject and the researchers are unaware of each subject's assignment until the completion of all data collection. This is accomplished using the randomization codes described above. Furthermore, this study utilizes an active sham stimulation. This means that the sham/placebo condition includes some stimulation, mimicking the skin sensations associated with tACS. Blinding success is tested on D5 with two separate questionnaires for operator and participant. In our

previously concluded trial, subjects in the sham and 10 Hz tACS groups responded similarly to the blinding questionnaire, indicating that our active sham stimulation successfully blinded the subjects.

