9.4.2 ANALYSIS OF THE PRIMARY EFFICACY ENDPOINT(S) (EEG)

We will perform spectral analysis of resting state EEG from day 1 of stimulation (baseline), day 5 of stimulation, and the 2-week follow-up visit. We will use a repeated measure ANOVA and/or a general linear mixed-effects model (GLMM) to assess if there is statistically significant interaction between treatment (sham/placebo and 10 Hz tACS) and session (baseline, day 5 of stimulation, 2-week follow-up). In the case of missing data (e.g., missing follow-up visits), analysis using a GLMM will be prioritized, as GLMM takes into account missing data. Spectral analysis will be performed with multi-tapered estimation of the frequency spectrum followed by integration over the classical alpha EEG band (8-12 Hz).

In a separate analysis, we will perform spectral analysis of resting state EEG before and after each separate stimulation session. These analyses will be completed on the modified intention-to-treat dataset. Results from this section will be described in mean decibel (dB) change and presented using spectral images for visualization.

9.4.3 ANALYSIS OF THE SECONDARY ENDPOINT(S)(CORRELATION BETWEEN EEG CHANGES AND SYMPTOMS OF DEPRESSION)

Using the EEG results described in 9.4.2, mean dB change from baseline will be correlated with normalized change in HDRS17 scores.* Correlations will be assessed using Pearson's r and data will be plotted against the best fit line to visualize the results.

*HDRS17 normalization:

$[[\text{HDRS17 score at Visit \#}] - [\text{HDRS17 score at baseline}]] / [\text{HDRS17 score at baseline}]$

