10.1.7.1 THE CAROLINA CENTER FOR NEUROSTIMULATION MONITORING PLAN

The latest version of the approved IRB application for this clinical trial will be followed at all times. This responsibility falls in the hands of the trained research personnel. If at any time there is a deviation from protocol, the deviation form protocol log will be filled out. All team members will be trained on how and when to use this log.

Data will be verified for completeness following every study session and all data will be entered into REDCap, a secure online database. After a subject has completed their participation (full completion through the 2-week follow-up visit or because they withdrew prior to completion), data will be rereviewed for completeness and accuracy. After all data has been collected, data will be re-reviewed by another lab member who was not involved with the data collection process.

AE and SAE are clearly defined in the Master Protocol. Documents of AE and SAE can be found in the study binder on file within [name]. It is responsibility of

trained research personnel to report all events to the PI. Reporting of AEs and SAEs is described within **Section 8.3**.

The PI and Co-I will have read-only access to the REDCap database. This allows the PI and Co-I to view reports that provide information on any missing data on an individual subject basis, but does not allow them to add, change or input any data.

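### The blind is guaranteed only until data collection ends; nothing requires the primary EEG endpoint to be derived, or the final data re-review done, blind to arm

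*Combined protocol and SAP*

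**What the plan says.** Two sections define the blind, and both end it at the same point. Section 6.3: "This means that the subject and the researchers are unaware of each subject's assignment until the completion of all data collection". Section 4.2: "All individuals involved with data collection (as well as all randomized subjects) will be blind to the subject's arm assignment", and this lasts "until all data has been collected". Section 4.2 also gives the purpose: "This will reduce implicit and explicit bias in the data collection process". People who process or analyse the EEG are not named.

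Section 9.4.2 describes the derivation of the primary endpoint: "Spectral analysis will be performed with multi-tapered estimation of the frequency spectrum followed by integration over the classical alpha EEG band", with the band set at 8-12 Hz. It does not say who does this, when, or whether they are masked.

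Section 10.1.7.1 describes three rounds of data checking. The first follows each session: "Data will be verified for completeness following every study session and all data will be entered into REDCap". The second follows each participant's exit. The third comes last: "After all data has been collected, data will be re-reviewed by another lab member who was not involved with the data collection process".

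**The concern.** In a trial whose outcome is recorded at the visit, a blind that ends with data collection covers the measurement. Here the recording is made at the visit, but the outcome is the product of later processing. Someone decides which segments to discard, which of the day's recordings to use, which channels to average, whether to transform, and which model to report. If these decisions are made after the codes are released, the double blind covers acquisition of the EEG but not its reduction to a result.

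The stakes are higher because the laboratory has a direction in mind. Section 2.2 reports that its earlier trial found a reduction in left frontal alpha where other groups found increases, and section 9.2 expects a significant difference. With 10 participants per arm, a few decisions can matter.

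**Working it through.** **1. Timing, side by side.** The plan states no figure on this point, so the check is mainly one of wording.

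| Step | When, according to the plan | Blind guaranteed? |
|---|---|---|
| EEG acquisition, ratings | During participation (8.1) | Yes (4.2, 6.3) |
| Check after each session | During collection (10.1.7.1) | Yes |
| Review after each participant exits | During collection for all but the last participant (10.1.7.1) | Yes, except possibly for the last |
| EEG preprocessing and alpha-power derivation | Not stated (9.4.2) | No |
| Choice of transformation and model | Not stated (9.4.1, 9.4.2) | No |
| Final re-review | After all collection (10.1.7.1) | No |

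The final re-reviewer is by definition not a data collector, so the wording of 4.2 does not cover that person at all. No section provides for a masked analyst, a lock before code release, or a dated unblinding step.

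**2. What is fixed and what is open.** Section 9.4.2 fixes the multi-taper method, the band, the three sessions and the treatment-by-session interaction. It leaves open:
- artefact rejection (no rule is given);
- channels or region (none is named, although the synopsis specifies high-density EEG);
- the Day 5 recording. Section 8.1.1 has one before and one after stimulation. The hypothesis in 9.1 points to the completion of stimulation, but 9.4.2 names only the day;
- transformation, which 9.4.1 leaves to judgement;
- the model: ANOVA, mixed model or both, with the mixed model favoured if data are missing.

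**3. Sensitivity of a 10-versus-10 comparison (shift assumed).** Inputs are 10 per arm (9.2), threshold 0.05 (9.4.1), two-sided by assumption, and a two-sample t-test with 18 degrees of freedom. The smallest significant difference is 2.101 × √(2/10) = 0.94 SD. If arm-aware handling moved the between-arm difference by b SD, the type I error would be P(|T| > 2.101), with T noncentral t and noncentrality b/√(2/10):

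| Assumed b (SD) | Type I error |
|---|---|
| 0.10 | 5.5% |
| 0.25 | 8.3% |
| 0.50 | 18.5% |
| 0.75 | 35.5% |

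The documents give no value for b.

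**4. Selection among variants (variants and correlations assumed).** The simulation ran 20,000 null trials, 10 per arm, with a t-test on change. There were 2 Day 5 recordings × 2 channel sets × 2 cleaning settings = 8 variants. The correlation between two variants is the product of the correlations for the factors on which they differ.

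| Correlations (recording, channels, cleaning) | At least one variant p<0.05 |
|---|---|
| 0.5, 0.5, 0.9 | 22.9% |
| 0.7, 0.7, 0.9 | 19.3% |
| 0.8, 0.8, 0.95 | 15.6% |
| 0.9, 0.9, 0.95 | 12.9% |

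One variant fixed in advance gives about 5%. With recording and channels fixed and only cleaning free, the figure is about 6 to 8%. Counting only significance in the expected direction over all eight variants gives about 6.5 to 12%, against 2.5% nominal. Most of the 13 to 23% therefore comes from recording and channels not being named, which is a prespecification gap that exists whenever the blind is lifted.

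**The case against.** The strongest reply is that the plan nowhere says EEG will be processed unblinded. That is correct. With 20 participants in a study planned to last two years, processing each one on exit, still under the blind, fits the text. A sentence in 5.5 even has session data scored on the same day, though it concerns retention and may not refer to EEG. What stands is that the order is unknown. What does not follow is that the order is safe, because the only written rule allows release of the codes before processing.

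A second reply is that the code holder is independent (6.3). That protects the blind during collection, but it does not delay release of the codes until processing is done.

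A third is that band power is computed by algorithm and much of it is fixed. This stands in part. A reader might infer that every judgement behind the primary outcome is exposed, but 9.4.2 rules that out. The exposure is limited to the open steps listed above.

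Three other inferences are tempting and unsupported:
- That the last round of data corrections is unblinded. Section 10.1.7.1 describes a re-review and mentions no corrections.
- That adverse-event rating falls outside the blind. Sections 8.2.3 and 10.1.6 place the assessments during participation, so at most a few late reports could.
- That the harm would be irreversible. Sections 10.1.4 and 10.1.9.2 provide for archiving and five years' retention. If the raw EEG is kept, it could be reprocessed blind.

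**Conclusion.** The concern holds as a gap in what the plan guarantees. Sections 4.2 and 6.3 end the blind at a point that need not follow derivation of the primary endpoint, the final re-review is placed after that point, and nothing requires either to be masked. The plan permits arm-aware choices on the open steps. It does not require them, and the documents do not show that they will occur.

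The size of any bias cannot be derived from the documents. The 13 to 23% rests on assumed variants and correlations, uses a t-test on change instead of the planned three-session interaction, and is an upper bound for selection. A reader might take it as the price of the unblinding date, but with only the cleaning step free it falls to about 6 to 8%. The conclusion depends on the wording and on none of these figures. Because the EEG result is the purpose of the trial and the correction is nearly free, the change should be made before any codes are released.

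**What to change.** In 4.2 and 6.3, replace the clause that dates the end of the blind (in 4.2, "until all data has been collected") with: *until EEG preprocessing, choice of recordings and channels, alpha-power extraction, choice of transformation and primary model, and the data re-review in 10.1.7.1 are complete and the dataset is locked.* Add that EEG files are processed under the participant code, and that the existing code holder releases the list to the analyst only after the dated lock.

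This needs no new staff, visit or procedure, because the independent code holder (6.3) and coded data (10.1.3) already exist. The only downside is that unblinding comes slightly later. Naming the recordings and channels in 9.4.2 is a separate matter; this change protects those choices from knowledge of arm but does not replace specifying them.
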